9.4.1.1. Primary Efficacy Analysis

For the primary endpoint of the proportion of subjects who experience worsening of asthma by Week 24, logistic regression modeling will be used to compare each GB001 group with placebo. The model will include factors for treatment group, baseline ICS dose (medium or high), region (pooled country), baseline FEV₁, and baseline ACQ-5. Odds ratios (ORs), p-values, and corresponding 95% confidence intervals (CIs), along with the absolute differences and corresponding 95% CIs, will be summarized for each GB001 group versus placebo.

A subject who prematurely withdraws from the study without experiencing asthma worsening will be assigned asthma worsening status by Week 24 (yes/no) based on their IP discontinuation and study withdrawal reasons. If a subject's reason for IP discontinuation or study withdrawal is indicative of lack of efficacy or is an AE indicative of asthma worsening, a determination will be made prior to study unblinding regarding whether the subject should be considered to have had asthma worsening for the primary endpoint. Otherwise, subjects who prematurely withdraw from the study will be considered to have not experienced asthma worsening for the primary endpoint. Details of handling of missing data for the primary endpoint will be fully described in the SAP.

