2.5. Sample Size Determination

A total sample size of approximately 480 subjects (approximately 120 per treatment group, randomized in a 1:1:1:1 ratio) is estimated to provide 80% power to detect a reduction in odds of 66% between each GB001 group and placebo at an 0.050 two-sided level of significance for the primary endpoint of the proportion of subjects who experience worsening of asthma by Week 24. This assumes the proportion of subjects who experience worsening of asthma by Week 24 is 25% in the placebo group and 10.2% in each GB001 group and a dropout rate of 8%.

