8.1.3. Multiple Comparisons/Multiplicity

In general, statistical testing of efficacy endpoints will be made without any adjustments for multiplicity, and all statistical hypothesis tests will be two-sided with a significance level of 0.050.

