8.3. Analysis Methods

8.3.1. Primary Efficacy Analyses

The primary endpoint is the proportion of subjects who experience worsening of asthma by Week 24 as defined by at least one of the following:

- On 2 consecutive days, AM PEF \leq 75% of mean AM PEF measured over the last 7 days of the Run-in
- $FEV_1 < 80\%$ of baseline (Visit 2)
- Increase in rescue medication use of ≥ 6 puffs/day on 2 consecutive days compared to mean use over the last 7 days of the Run-in
- Increase in ACQ-5 score of ≥ 0.5 compared to baseline (Visit 2)
- The occurrence of a severe asthma exacerbation (asthma attack) defined as deterioration of asthma that leads to the use of systemic corticosteroids for at least 3 days, hospitalization, or an Emergency Department visit

Logistic regression modeling will be used to compare each GB001 group with placebo. The model will include covariates for treatment group, ICS dose (medium or high) at randomization, region (North America, Eastern Europe, Western Europe), baseline pre-bronchodilator FEV₁, and baseline ACQ-5 score. If the full model does not converge, a model with treatment group, ICS dose at randomization, and region as covariates will be utilized. If this reduced model does not converge, a model with treatment group and ICS dose at randomization will be used. In the rare case that convergence issues remain, only treatment group will be included in the model.

The number and proportion of subjects meeting the primary endpoint and corresponding 95% Wilson (Score) CIs (Wilson, 1927) will be summarized by treatment group. ORs, corresponding asymptotic 95% CIs along with the absolute differences and corresponding 95% CIs, and p-values will be summarized for each GB001 group versus placebo. The 95% CIs for the absolute difference will be Newcombe continuity-corrected CIs (Newcombe, 1998). Percentage reductions and corresponding 95% CIs will also be summarized. Lastly, the number and proportion of subjects meeting each component of the primary endpoint, with observed worsening of asthma, and with an assigned status of asthma worsening will also be summarized by treatment group. Subjects can meet more than one component of the primary endpoint.

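### The absolute risk difference gets an unadjusted, continuity-corrected interval beside a covariate-adjusted test: a minor loss of precision and an occasional mismatch that the SAP does not address

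*SAP*

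**What the plan says.** SAP 8.3.1 compares each dose with placebo by logistic regression on treatment, ICS dose at randomization, region, baseline pre-bronchodilator FEV1 and baseline ACQ-5. It lists odds ratios with asymptotic intervals, "along with the absolute differences and corresponding 95% CIs, and p-values will be summarized for each GB001 group versus placebo". For the difference it then specifies: "The 95% CIs for the absolute difference will be Newcombe continuity-corrected CIs". The proportion in each arm is treated differently, with "corresponding 95% Wilson (Score) CIs (Wilson, 1927) will be summarized by treatment group" and no continuity correction mentioned.

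Protocol 9.4.1.1 asks for the odds ratios and p-values "along with the absolute differences and corresponding 95% CIs, will be summarized for each GB001 group versus placebo", but names no interval method for the difference.

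Neither document labels the difference as unadjusted, or says which result to rely on if the interval and the p-value point different ways. Neither makes the risk-difference interval a decision criterion. SAP 8.1.3 says that "all statistical hypothesis tests will be two-sided with a significance level of 0.050", in general without multiplicity adjustment, so the reader will see three such comparisons.

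**The concern.** The odds ratio and the risk difference describe the same comparison but come from different estimators. The odds ratio and its p-value use the baseline covariates. The risk difference discards them and adds a continuity correction. The absolute difference is the measure most readers will use to judge clinical size, so it matters that its uncertainty is somewhat overstated.

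The visible consequence is a table row in which the adjusted p-value is below 0.05 while the risk-difference interval includes zero. The SAP gives no rule for reading such a row.

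**Working it through.** **Inputs.** From SAP 2.5: 120 per arm, 25% vs 10.2%, 8% dropout, two-sided 0.050. The interval method and the model are from SAP 8.3.1. The documents do not give the prognostic strength of the covariates. I assume a standard deviation (SD) for the covariate part of the log-odds and vary it from 0 to 1.5.

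**1. The plan's own figure.** SAP 2.5 says the sample size "is estimated to provide 80% power to detect a reduction in odds of 66% between each GB001 group and placebo".

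- OR = (0.102/0.898)/(0.25/0.75) = 0.341, a 66% reduction in odds; log OR = −1.0766.
- With 120 × 0.92 ≈ 110 per arm, SE = √[1/(110 × 0.25 × 0.75) + 1/(110 × 0.102 × 0.898)] = √(0.0485 + 0.0993) = 0.3844.
- Power = Φ(1.0766/0.3844 − 1.960) = Φ(0.841) = 0.80.

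The figure reproduces, and it does not involve the risk-difference interval.

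**2. The interval.** With d = p1 − p0 and score limits (l, u) for each arm, Newcombe's limits are d − √[(p1 − l1)² + (u0 − p0)²] and d + √[(u1 − p1)² + (p0 − l0)²]. No covariate enters. Example: 12/120 on GB001 against 30/120 on placebo, d = −0.150.

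- Uncorrected score limits are 0.0581 to 0.1667 and 0.1811 to 0.3344. Lower: −0.150 − √(0.0419² + 0.0844²) = −0.244. Upper: −0.150 + √(0.0667² + 0.0689²) = −0.054.
- Continuity-corrected score limits are 0.0550 to 0.1716 and 0.1775 to 0.3389. Lower: −0.150 − √(0.0450² + 0.0889²) = −0.250. Upper: −0.150 + √(0.0716² + 0.0725²) = −0.048.

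**3. Effect of the correction alone.** I enumerated both binomials exactly at 120 per arm and the planning rates. Mean width is 0.201 corrected and 0.190 uncorrected (0.2011/0.1897 = 1.06). Coverage is 96.4% and 95.2%. The uncorrected interval also ignores the covariates yet covers at the nominal level, so the excess coverage comes from the correction.

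**4. Effect of ignoring the covariates.** I simulated the four-arm trial with the SAP's model (2,000 trials per row, planning rates, one dose against placebo; ICS dose and region non-prognostic). The standardized difference averages the model's predicted risks over all subjects under each treatment, with a delta-method standard error.

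| Covariate SD | Width, planned CI | Width, standardized CI | Ratio | p<0.05, planned CI includes 0 | p≥0.05, planned CI excludes 0 |
|---|---|---|---|---|---|
| 0 | 0.2010 | 0.1879 | 1.07 | 2.2% | 0.25% |
| 0.5 | 0.2014 | 0.1848 | 1.09 | 3.5% | 0.55% |
| 1.0 | 0.2010 | 0.1751 | 1.15 | 7.55% | 1.05% |
| 1.5 | 0.2013 | 0.1639 | 1.23 | 9.7% | 0.55% |

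The Monte Carlo standard error of the fifth column is about 0.3 to 0.7 points. A separate run of 3,000 trials gave 4.3% and 7.4% at SD 0.5 and 1.0. At an assumed 45% vs 30%, which is not a planning rate, it gave 6.9% and 13.7%.

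**5. Dropping only the correction.** At SD 0, 0.5, 1.0 and 1.5, p<0.05 with an interval including zero falls to 0.5%, 2.05%, 5.15% and 7.6%. The reverse conflict becomes 1.15%, 1.05%, 1.55% and 0.75%. Coverage returns to nominal, but the mismatch with the adjusted test remains.

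**6. The standardized interval.** It disagrees with the adjusted p-value in 0.4% to 0.9% of comparisons at the planning rates. In the 3,000-trial run it never included zero when p<0.05, and its coverage was 94.2% to 95.0%.

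**The case against.** The planned interval is a named, referenced, prespecified method whose coverage is above its nominal level. In the example above, −0.250 to −0.048 and −0.244 to −0.054 would be read the same way. A crude difference also equals the subtraction of the tabulated proportions; a standardized one generally does not. Its covariate set cannot change, whereas a model-based difference would follow the SAP's convergence fallbacks. The comparison of doses with placebo rests on the logistic model, and nothing is decided on the risk-difference interval.

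All of this stands, and it limits the point to reporting. It does not remove it. The uncorrected interval already covers nominally at the planning rates, so the correction buys nothing there. The per-arm intervals are not described as corrected. The covariates are already in the fitted model, and sensitivity analysis #4 (SAP 8.3.1.1.4) already calls for model-based proportions, so the approach is not foreign to the plan.

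A reader might infer that the interval will often contradict the p-value. The documents do not support that. At the planning rates p<0.05 with an interval including zero stays at or below 10% of comparisons even at SD 1.5. The figure near 14% needs both an assumed 45% vs 30% and SD 1.0. A reader might also infer that omitting the covariates inflates coverage; step 3 shows that it does not.

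**Conclusion.** The point holds as a minor issue of precision and reporting. At the planning rates the continuity correction makes the interval 6% wider and raises coverage from 95.2% to 96.4%. With the unused covariates, the interval is about 9% to 15% wider than a standardized one, if the covariate log-odds SD is 0.5 to 1.0. It would include zero beside an adjusted p below 0.05 in about 2% of comparisons with non-prognostic covariates and about 7% at SD 1.0.

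The width and coverage effects of the correction are exact for the stated rates and sample size. The other figures rest on an assumed covariate strength and on simulation.

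It would be wrong to conclude that the interval is invalid or that the primary analysis is compromised. The interval over-covers slightly, and the test, its type I error, its power and the odds ratio with its interval do not depend on it.

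**What to change.** In SAP 8.3.1:

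1. Report the marginal (standardized) risk difference from the primary logistic model, with a delta-method or bootstrap 95% CI, as the main absolute measure. State that it uses whichever covariate set the convergence fallbacks leave.
2. Keep the crude difference with a Newcombe interval without continuity correction, matching the per-arm Wilson intervals, and label it unadjusted and descriptive.
3. State that the logistic p-value governs if an interval and the test disagree.

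Items 2 and 3 alone would restore nominal coverage and tell the reader how to resolve a conflict, but would not recover the lost precision.

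The cost is a few lines of programming on a model already fitted. Protocol 9.4.1.1 names no interval method, so its text need not change. There are small downsides. Delta-method coverage can fall slightly below 95% (about 94% to 95% in simulation), and a bootstrap interval is the alternative if that is a concern. The standardized interval can exclude zero when the adjusted p is 0.05 or above in about 1% of comparisons. The standardized difference will not exactly match the subtraction of the tabulated percentages, so a footnote should say so. The change belongs before unblinding. If made later, SAP section 1 requires supplementary analyses to be identified as post hoc.

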Subjects will be provided with an eDiary which is programmed to alert the subject of potential asthma worsening:

1. On 2 consecutive days, AM PEF \leq 75% of mean AM PEF measured over the last 7 days of the Run-in period
2. Increase in rescue medication use of \geq 6 puffs/day (last 24 hours) on 2 consecutive days compared to mean use over the last 7 days of the Run-in period
3. Nighttime awakening due to asthma symptoms requiring rescue medication for at least 2 of 3 successive nights
4. An asthma symptom score of 4 for at least 2 of 3 successive days.

Upon receiving an alert, the subject should contact the site staff as soon as practical to assess the subject's asthma status. The subject may be asked to return to the clinic when necessary to have their asthma status evaluated.

Subjects who permanently discontinue IP will be requested to attend the Early Discontinuation of IP visit and will be strongly encouraged to complete any remaining study visits as per the Schedule of Activities (SoA; [Section 1.3](#)). Subjects who permanently discontinue IP and continue in the study will complete the Early Discontinuation of IP visit at the time of IP discontinuation and then return for the next visit in the Double-Blind, Placebo-Controlled visit sequence. At the visits subsequent to the Early Discontinuation of IP visit, study procedures will be completed except for dispensation/return of IP. Subjects who withdraw from the study, regardless of the reason, will be requested to return to the clinic to complete the Early Withdrawal (EW) from Study visit. All subjects who remain on IP through and including Visit 9 (Week 24) or who complete the EW from Study visit will be asked to return for a Follow-up visit approximately 4 weeks after their last dose of IP to assess subject safety.

Total duration for study participation per subject is up to 34 weeks (includes a Screening visit, followed by a 2-week to 6-week Run-in period to allow for collection of baseline eDiary data; a 24-week Double-Blind, Placebo-Controlled period; and 4-week Follow-up period).

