9.5. Interim Analyses

An unblinded interim analysis will be conducted after the first 320 subjects have completed the study or have prematurely withdrawn from the study. The purpose of this interim analysis is to inform further development of GB001. The interim analysis will consist of a comprehensive assessment of GB001's benefit-risk profile, including, but not limited to, evaluation of primary and secondary efficacy endpoints and safety outcomes.

The interim analysis will be performed and reviewed by select unblinded Sponsor (or designee) personnel who will not be directly involved in the conduct of the study following the interim analysis and the IDMC. Subjects, Investigators and other site personnel, and Sponsor (or designee) personnel who remain directly involved in the conduct of the study following the interim analysis will remain blinded to treatment assignment throughout, until after the completion of the study. Details of the select unblinded Sponsor (or designee) personnel and measures to ensure rigorous maintenance of the blind will be provided prior to unblinding as part of an interim statistical analysis plan.

Given that the interim analysis is administrative, will not result in any statistical inferences being made, and is not intended to result in any modification to the study (ie, the study will be continued and completed regardless of the interim analysis results), no Type I error will be allocated to the interim analysis.

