A subject who prematurely withdraws from the study without experiencing asthma worsening will be assigned asthma worsening status by Week 24 (yes/no) based on their discontinuation of study treatment and withdrawal from study reasons as summarized below in Table 2. If a subject's reason for discontinuation of study treatment or withdrawal from study is indicative of lack of efficacy or is an AE indicative of asthma worsening, a determination will be made prior to study unblinding for the interim analysis regarding whether the subject should be considered to have had asthma worsening for the primary endpoint. Otherwise, subjects who prematurely withdraw from the study will be considered to have not experienced asthma worsening for the primary endpoint.

Table 2:Criteria for determination of asthma worsening status for subjects who
prematurely withdraw from the study without experiencing asthma
worsening

Reason for Discontinuation of Study Treatment and/or Withdrawal from Study	Asthma Worsening Status Assigned (Yes/No)
Lack of Efficacy	Yes
AE where the corresponding AE PT reflects asthma worsening including 'asthma'	Yes
Death where death is due to an SAE where the corresponding SAE PT reflects asthma worsening including 'asthma'	Yes
Lost to follow-up, Non-compliance with study drug, Physician decision, Protocol deviation, Withdrawal by Subject, or Other, where further details indicate asthma, asthma worsening, lack of efficacy or prescription of or switch to a new asthma treatment	Yes
AE where the corresponding AE PT does not reflect asthma worsening	No
Death where death is due to an SAE where the corresponding PT does not reflect asthma worsening	No
Lost to follow-up, Non-compliance with study drug, Physician decision, Protocol deviation, Withdrawal by Subject, or Other, where further details do not indicate asthma, asthma worsening, lack of efficacy or prescription of or switch to a new asthma treatment	No

A bar graph of the proportion of subjects meeting the primary endpoint by treatment group and a bar graph of the proportion of subjects meeting each component of the primary endpoint by treatment group will be provided.

The primary endpoint and components will also be presented in a by-subject data listing.

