8.3.2.2. Time to First Asthma Worsening

Time to first asthma worsening is defined as the time from the date of the first dose of study treatment to the first date that any of the components of the asthma worsening endpoint is met. Subjects who do not experience asthma worsening will be censored on the date of their last assessment for any of the components of asthma worsening. For the primary analysis of time to first asthma worsening, all data up to Week 24 will be utilized; a sensitivity analysis of time to first asthma worsening will be performed utilizing all data up to the Follow-up Visit (Week 28).

For subjects who experience asthma worsening, the date of the event is defined for each component as:

- AM PEF and rescue medication use date of event is considered to be on the first of 2 consecutive days where the respective criterion is met
- FEV₁ and ACQ-5 score date of event is considered to be on the date of the qualifying assessment
- Severe exacerbation date of event is considered to be on the date of onset of exacerbation as captured on the Severe Asthma Exacerbations eCRF

The number and proportion of subjects with asthma worsening will be summarized. The number and proportion of subjects meeting each component will also be summarized with subjects counted only once for the component first met.

Time to asthma worsening will be compared between treatment groups using a Cox proportional hazards model. The exact method will be used to handle ties in event times. Covariate adjustment will be the same as for the primary endpoint. Estimates of the hazard ratio for each GB001 group versus placebo, corresponding 95% CIs, and p-values will be provided from the model. Percentage reductions and corresponding 95% CIs will also be provided. Kaplan-Meier summaries of the proportion of subjects with asthma worsening over time will also be presented and displayed graphically. The median event time (and other quartiles), if estimable, and corresponding 95% CI based on the Brookmeyer and Crowley method (Brookmeyer, 1982) will be provided for each treatment arm.

Time to asthma worsening data will also be presented in a by-subject data listing.

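### Withdrawals assigned asthma worsening by SAP Table 2 have no event date in the time-to-event analysis, and subjects who withdraw after the interim cannot meet the deadline for that assignment (minor)

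*SAP*

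**What the plan says.** **Primary analysis (SAP 8.3.1).** A subject who leaves the study without meeting a component receives a Yes or No status from Table 2. The table's first column is headed "Reason for Discontinuation of Study Treatment and/or Withdrawal from Study", so the reason for stopping investigational product (IP) can decide the status as well as the reason for leaving the study. Asthma-related reasons give Yes. For the rest: "Otherwise, subjects who prematurely withdraw from the study will be considered to have not experienced asthma worsening for the primary endpoint".

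**Timing of the decision.** The SAP says "a determination will be made prior to study unblinding for the interim analysis regarding whether the subject should be considered" to have worsened. Protocol 9.4.1.1 says "a determination will be made prior to study unblinding regarding whether the subject should be considered", with no reference to the interim. Protocol 9.5 places the interim after the first 320 subjects complete or withdraw, and states that "the study will be continued and completed regardless of the interim analysis results".

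**Time to first worsening (SAP 8.3.2.2).** The event is "the first date that any of the components of the asthma worsening endpoint is met", and the dating rules cover the components only. "Subjects who do not experience asthma worsening will be censored on the date of their last assessment" of any component. Table 2 status is not mentioned.

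**Sensitivity analysis #4 (SAP 8.3.1.1.4).** The yes/no outcome is imputed directly within treatment group, in an intermittent and then a monotone stage. No by-visit status is defined. The analysis runs only if at least 5% of all subjects lack an observed status.

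**The concern.** A Table 2 Yes subject has by definition met no component. The same person is therefore an event in the primary analysis and, on a literal reading, censored in the Cox and Kaplan-Meier analyses. The reason for censoring is lack of efficacy or asthma, so it is plausibly informative. The secondary analysis also uses a narrower event than the primary one under the same name. The only sensitivity analysis planned for it extends the window to Week 28, which does not address this.

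The deadline is a separate matter. A subject who withdraws after the interim unblinding cannot be decided before it. Most Table 2 rows are mechanical, but deciding whether further details point to asthma, or whether a preferred term reflects worsening, takes judgement. SAP 8.3.1 does not say who decides or when for these cases.

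A lesser point is that two programmers could implement #4 differently, with or without conditioning on the time a subject was event-free.

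**Working it through.** **Inputs (SAP 2.5; Protocol 9.2 and 9.5).** 120 per arm, worsening 25% v 10.2%, dropout 8%, two-sided 0.050, 80% power; interim at 320 of 480.

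**The plan's own figure.** OR = (0.102/0.898)/(0.25/0.75) = 0.341, a 66% reduction in odds. Evaluable n = 120 × 0.92 = 110.4. SE of log OR = √[1/(110.4×0.25×0.75) + 1/(110.4×0.102×0.898)] = 0.384. Power = Φ(1.077/0.384 − 1.96) = 0.80. The stated power reproduces.

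**1. Event date.** With constant hazards the planned rates imply HR = ln(0.898)/ln(0.75) = 0.374. The documents do not give the share of Table 2 Yes subjects, so it is assumed (1% is about 1 subject per arm). Simulation: 1,000,000 subjects per arm; Yes subjects meet no component, stop IP uniformly over Weeks 0-20 and leave the study 0 or 8 weeks later.

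| Yes share, placebo / GB001 | HR, censored | HR, counted as events |
|---|---|---|
| 1% / 1% | 0.37 | 0.39-0.40 |
| 2% / 2% | 0.37-0.38 | 0.41-0.42 |
| 3% / 3% | 0.37-0.38 | 0.43-0.44 |
| 4% / 1% | 0.38 | 0.36 |
| 1% / 3% | 0.37 | 0.46-0.47 |

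Allowing for variation between runs, the counted version lies between about 0.35 and 0.48. At 2%/2% the primary proportions are 0.02 + 0.98×0.25 = 26.5% and 0.02 + 0.98×0.102 = 12.0%. The Week 24 Kaplan-Meier estimates with censoring are about 24.8% and 10.1%; with these subjects counted as events they agree with the primary proportions. When IP stops 8 weeks before withdrawal, choosing one date rather than the other moves the HR by at most 0.006.

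**2. Deadline.** At the interim trigger 480 − 320 = 160 subjects are still in the study or not yet randomized. At 8% dropout that is 160 × 0.08 = 12.8, about 13 withdrawals. This is an upper bound, because some may withdraw between the trigger and the unblinding, and Table 2 applies only to those without worsening. If 1-3% are assigned Yes, that is 160 × 0.01 to 160 × 0.03, about 2 to 5 subjects.

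**3. Sensitivity #4 at planning values.** Constant event hazard λ = −ln(1−p)/24 and dropout hazard μ = −ln(0.92)/24 give:

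- Observed events = [λ/(λ+μ)] × [1 − 0.92(1−p)]: 24.0% placebo, 9.8% GB001.
- Missing status = [μ/(λ+μ)] × [1 − 0.92(1−p)]: 7.0% and 7.6%. Overall (7.0 + 3×7.6)/4 ≈ 7.4%, above the 5% trigger.
- Risk among subjects with an observed status: 25.8% and 10.6%.
- Imputed directly, the proportions are 25.8% v 10.6%, OR 0.340. Imputed conditional on event-free time, they are 25.0% v 10.2%, OR 0.341.

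The trigger can miss an imbalance confined to one arm. With no drug effect, 25% risk and assumed uniform withdrawal of 2%, 2%, 2% and 16%, 4.8% are missing and #4 is skipped, while that arm's primary OR is 0.91.

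**The case against.** **The censoring may be deliberate.** SAP 8.3.2.2 defines the event explicitly, and SAP 8.3.1 tabulates observed and assigned worsening separately, so the difference would be visible. That is fair, but the SAP does not say the two analyses are meant to differ.

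**The group is small.** Early-discontinuation and early-withdrawal visits include ACQ-5, spirometry and eDiary review, which can supply a dated component. Protocol 8.3.6 records asthma worsening as an adverse event only when serious, and a hospitalization or emergency visit is already a component. The HR shifts are also small against sampling error: with about 30 v 12 events the 95% interval is roughly 0.19-0.73. All of this stands and limits the severity.

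**Stronger readings a reader might infer.**

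- *The SAP contradicts the protocol on timing.* It does not. Before the interim unblinding is also before study unblinding, so the SAP is stricter. The defect is that its rule cannot be met for late withdrawals.
- *Late cases would be classified unblinded.* The documents do not say so. Protocol 9.5 keeps study-conduct staff blinded, and the criteria in Table 2 are fixed in advance. The separate interim plan is not available here.
- *Censoring favours GB001.* The direction depends on the arm split; at 4%/1% it goes the other way.
- *The No default, or #4 imputed directly, seriously distorts the result.* With no drug effect and balanced withdrawal the primary OR is 1.00. At 5% placebo and 9% GB001 withdrawal the primary rule gives 0.97 and #4 imputed directly gives 1.02, so they err in opposite directions, #4 against the drug. The Cox analysis and sensitivity analyses #1-#3 have no 5% trigger.

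**Conclusion.** The concern holds, at minor severity, as two gaps in the SAP.

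1. Table 2 Yes subjects have no event date in SAP 8.3.2.2 and, read literally, are censored there although they count as events in the primary analysis. For assumed shares of 1-4% this is the difference between an HR of about 0.37 and one of about 0.35-0.48. Those figures rest on constant hazards and on shares that the documents do not supply.
2. The interim deadline cannot be met for between 0 and about 13 later withdrawals, of whom fewer need judgement.

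The undefined visit sequence and pooled trigger of #4 are worth tidying, but they are not a reason to act by themselves: at planning values the OR changes by 0.001, and #4 would run.

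**What to change.** **1. SAP 8.3.2.2.** Add: *Subjects assigned asthma worsening by Table 2 are counted as events on the date of study withdrawal.* Report the component-only, censored version as a sensitivity analysis. Every Table 2 subject has left the study, so the date always exists. The IP stop date is less suitable because "Subjects who permanently discontinue IP and continue in the study will complete the Early Discontinuation of IP visit at the time of IP discontinuation", and an event dated there could contradict later follow-up in which no component was met. Cost: one sentence and one extra Cox run.

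**2. SAP 8.3.1.** Replace the timing with: *The determination will be made by personnel who remain blinded, before the interim unblinding for subjects already withdrawn and before final unblinding for all others.* Cost: one sentence; it stays within the protocol's wording.

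**3. Optional, SAP 8.3.1.1.4.** Run #4 without the 5% trigger and state that imputation is conditional on being event-free up to withdrawal. Cost: modest programming and sparse data. 10.2% of 120 is about 12 events per GB001 arm, under 2 for each of the seven intervals ending at Weeks 2, 4, 8, 12, 16, 20 and 24, so intervals may need pooling.

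None of these needs a protocol amendment.
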